Subjects will be excluded if they had previous brain surgery or other severe neurological problems – intracerebral hemorrhage, traumatic brain injury, central nervous system malignancy, active CNS infection, significant stroke, Alzheimer disease or any type of implanted stimulator including but not limited to Deep Brain Stimulator (DBS) or pacemaker. All subjects must be without evidence of dementia, defined as a score > 24 the Mini-Mental State Examination and able to understand test instructions. Subjects must not have functional blindness (inability to participate in gait and visuomotor assessments) or lower limb amputation higher than the forefoot or any orthopedic problem that precludes performance of physical tests. Allergic to niacin. Significant cardiac, pulmonary, hepatic, gastrointestinal, or renal disease (e.g., New York Heart Association Class III or IV congestive heart failure; endocarditis; pulmonary insufficiency symptomatic at rest or with mild physical exertion; acute or chronic hepatitis; renal failure requiring dialysis; second and third degree AV block or sick sinus syndrome), or diabetes are also exclusionary factors.

4. Number of Subjects/Records/Samples Collected

Indicate the total number of subjects to be accrued/records reviewed/samples collected across all sites:

100

5. Recruitment Methods

Describe when, where, and how potential subjects will be recruited:

VA clinic (including medical records), word of mouth.

6. Procedures Involved

a. *Describe the procedures involved to include those procedures that are standard evaluation and/or care and those that are solely for research purposes:*

Standard procedures: basic physical examination for strength, speed, coordination, tremor, flexibility, rigidity and reaction time

Research procedures: questionnaire and tests to document health and cognitive status, blood, urine and spinal fluid samples, over-the-counter (non-prescription) vitamin B3 supplementation

b. Describe and explain the study design: Pre-post repeated measures placebo-controlled study

c. Describe the procedures performed to lessen the probability or magnitude of risks: Use of slow-release supplement to minimize potential skin itching

d. Describe the duration of an individual subject's participation in the study and the time involved: 6 months supplement study with a pre and post test, each lasting about 1 to 1.5 hr.

7. Data and Specimen Management

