Safety information will be collected by telephone calls or emails with the participants.

d. *Describe the frequency of data collection, including when safety data collection starts.*

Data will be collected by the researchers at baseline and the end of the study. Subjects will be instructed to contact the researchers as soon as possible if they experience any adverse events that they think is related to the study.

e. *Describe who will review the data.*

[name] will be the main person to review the data. He will consult with [name] or [name] if needed.

f. *Describe the frequency or periodicity of review of cumulative data.*

Cumulative data will be reviewed every month to ensure adherence to the approved protocol.

g. *Describe any conditions that trigger an immediate suspension of the research.*

If a subject reports an unexpected adverse event, the study will be suspended. The study will resume if it is determined that the event is unrelated to the study.

9. Withdrawal of Subjects

N/A

a. If applicable, describe anticipated circumstances under which subjects will be withdrawn from the research without their consent.
 
Click here to enter text.
	 N/A

b. If applicable, describe any procedures for orderly termination.
 
Click here to enter text.
	 N/A

c. If applicable, describe procedures that will be followed when subjects withdraw from the research, including partial withdrawal from procedures with continued data collection.
 
A subject who withdraws from the study on their own accord will be replaced by another. A subject who partially withdraws from procedures will remain in the study as long as they continue taking the supplement.
	 N/A

10. Risks to Subjects

a. List the reasonably foreseeable risks.

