Low-level temporary discomfort or pain during the blood and lumbar draw. Contraindications for the lumbar puncture: Although there are no absolute contraindications to performing the procedure, caution will be used in patients with the following conditions: 1) Possible raised intracranial pressure; 2) Thrombocytopenia or other bleeding diathesis (including ongoing anticoagulant therapy); 3) Suspected spinal epidural abscess. The side effects associated with lumbar puncture may include following: 1) Discomfort or pain during the procedure; 2) Bleeding into the spinal cord, particularly in people who take blood thinners or have a low platelet count (thrombocytopenia); 3) Temporary headache as a result of CSF leakage; 4) Infection; 5) Nerve damage; 6) Cerebral herniation; 7) Temporary back pain.

We will take a conservative approach in deciding which patient to include from the lumbar procedure. Overall, [name] will exercise his clinical judgment to exclude a subject from the procedure if, in his opinion, he feels that the subject presents with a set of conditions which renders them unsuitable for the procedure.

b. If applicable, describe any costs that subjects may be responsible for because of participation in the research.
 
Click here to enter text.
	 N/A

c. If applicable, describe risks to others who are not subjects.
 
Click here to enter text.
	 N/A

11. Potential Benefits to Subjects

Describe the potential benefits that individual subjects may experience from taking part in the research.

Niacin is an over-the-counter supplement. Our preliminary data indicates that PD patients will benefit from the supplementation. The dosage selected is 250 mg daily dose for 6 months. These dosages are low and do not produce any side effects. If at all, the PD patients will be benefitted by its actions. Subjects will be given a \$50 gift card for successfully completing the 6-month study. They will receive an additional \$100 if they participate in the spinal draw. At the end of the study, all subjects will receive the real niacin and be invited back for an optional follow-up assessment.

12. Confidentiality

Describe the procedures for maintenance of confidentiality.

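### The $50 payment is tied to undefined successful completion and 9c ties staying in the study to taking the supplement, which gives a reason to conceal stopping and no payment for a stopper's post-test

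*Combined protocol and SAP*

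**What the plan says.** All references are to the combined protocol and SAP.

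- **Section 11 (Potential Benefits to Subjects).** "Subjects will be given a \$50 gift card for successfully completing the 6-month study." No part-payment or payment per visit is stated. A further $100 is paid to subjects "if they participate in the spinal draw", and nothing links that sum to completion or intake. At the end, everyone is given real niacin and offered an optional follow-up.
- **Section 9c (Withdrawal of Subjects).** "A subject who partially withdraws from procedures will remain in the study as long as they continue taking the supplement." For full withdrawal: "A subject who withdraws from the study on their own accord will be replaced by another." No post-test is described for a subject who stops the supplement.
- **Sections 6b and 6d.** The design is a "Pre-post repeated measures placebo-controlled study", run as a "6 months supplement study with a pre and post test".
- **Section 7a.** UPDRS III is the primary pre- and post-treatment outcome, analysed by mixed model ANOVA with group and time. No analysis population or missing-data rule is given.
- **Section 8.** Safety contacts are made on the day after the pre-test and the day after the post-test. In between, subjects are asked to report events themselves.

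**The concern.** The comparison needs a month-6 UPDRS III from as many enrolled subjects as possible, including those who stopped the supplement. As worded, the payment appears to reward persistence, or a claim of persistence, and not attendance. That has two possible consequences:

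1. **Concealment.** A subject who stops at, say, month 3 and says so may lose the $50, while one who says nothing keeps it. The trial would then have a false picture of who took the supplement.
2. **Missing outcomes.** A subject who stops openly has no payment to attend for and, under 9c, apparently no post-test to attend.

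There is only one post-test, so a missed one removes that subject's whole change on the primary outcome. Replacing withdrawals restores the numbers but does not undo selective loss.

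**Working it through.** The plan gives no figure on this point to reproduce, so the check is mainly one of reading.

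**Step 1: does stopping forfeit the $50?** Section 11 makes payment depend on successful completion. Section 6d describes what is to be completed as a supplement study with two tests. Section 9c allows a partial withdrawer to stay on one condition, continued intake. A subject no longer in the study is hard to describe as having completed it successfully. Forfeiture is therefore the natural reading. It still rests on an undefined term joined to the converse of a sentence about partial withdrawal from procedures; no sentence states it.

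**Step 2: could stopping be concealed?** No pill count, diary, or other check of intake is described. Section 8f provides monthly review of cumulative data for adherence to the protocol, but 8d has the researchers collect data only at baseline and at the end. The incentive to conceal is a fair inference from Step 1.

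**Step 3: what causes the loss of post-tests?** For an open stopper, the natural reading of 9c already ends participation, whatever is paid. Section 9c is the main cause. The payment wording adds to it by attaching no money to attendance as such.

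**Step 4: power or bias?** With the planned 30 PD subjects per group (section 7b) and a two-sided 0.05 t-test, power under assumed post-test loss is:

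| Effect size in 7b | No loss | 10% loss | 40% loss |
|---|---|---|---|
| d = 1.46 (UPDRS motor) | above 0.999 | 0.9995 | 0.989 |
| d = 0.97 (sleep efficiency) | 0.959 | 0.938 | 0.807 |

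At the plan's own effect sizes, lost post-tests threaten bias more than power.

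**Step 5: illustration of bias from all selective loss in one arm.** Suppose a fraction m of one arm stops and is not assessed, and their UPDRS III change is worse than the persisters' by g points. The full-arm mean change is then worse than the persisters' mean by m × g:

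- m = 0.10, g = 3: 0.10 × 3 = 0.3 points
- m = 0.30, g = 5: 0.30 × 5 = 1.5 points

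Both m and g are assumptions. The result covers every cause of loss in that arm and does not isolate the part due to payment.

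**Step 6: cost of paying stoppers.** If 20% of the 60 PD subjects stopped (an assumption) and all attended: 0.20 × 60 = 12 subjects, and 12 × $50 = $600.

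**The case against.** The strongest reply is that the protocol never says stopping costs the $50. Section 6d makes attending the post-test a plausible meaning of completion, and the card might be paid to anyone who attends. The consent pages are not available to this review and may settle the matter. This stands: forfeiture cannot be stated as fact. It does not remove the point, because the term is undefined in the protocol and its natural reading penalises disclosure.

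A reader might also infer three stronger things that the documents do not support:

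- **That the payment gives a reason to skip the post-test.** Nothing penalises attendance. A payment at month 6 and real niacin at the end both encourage subjects to reach it. At most, an open stopper lacks a payment.
- **That 0.3 to 1.5 points is the bias caused by the payment wording.** The share due to payment is unknown and could be near zero. Loss could also occur in both arms and partly offset. Differential loss is possible but not documented: section 6c mentions potential itching and a slow-release product to limit it, while section 11 says there are no side effects.
- **That safety reporting is corrupted.** Section 8 provides next-day contacts and a 24-hour hotline, and no text ties payment to silence about an adverse event.

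It is also fair to object that rewording section 11 alone would pay subjects for a visit that 9c does not appear to give them. That stands, so both sections need to change.

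**Conclusion.** The point holds in limited form. Its firmest part is the incentive to conceal stopping; the absence of any payment for a stopper's attendance is secondary to the 9c retention rule. It rests on reading section 11 and 9c together, and on the absence of any described intake check. No magnitude can be assigned, so the Step 5 figures serve only to show how selective loss in general would act on a single-post-test outcome. The change is worth making because it affects who supplies the primary outcome and removes a reason to hide non-adherence at little cost. It is a minor improvement, not a flaw that invalidates the design.

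**What to change.** 1. **Section 11 and the consent form.** State that the $50 is paid for attending the 6-month post-test, whether or not the supplement was taken throughout. Say that neither stopping it nor reporting that it was stopped affects payment. This replaces the undefined condition of successful completion.
2. **Section 9c.** Amend to match: subjects who stop the supplement but do not withdraw consent are still invited to the post-test, and their intake is recorded.

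These changes concern data collection and payment only, not treatment. They cost a few sentences in two sections and the consent form, plus at most $50 and one already planned visit of about 1 to 1.5 hours for each stopper who attends.
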